**v. TIME OF ENLISTMENT**

Participation in this HF will be offered to patients who meet the inclusion criteria during their postoperative follow-up visit.

**vi. TIMING OF RANDOMIZATION**

The CI design is not applicable and does not include the use of a comparator or comparison arm, so there can be no randomized assignment to any of these arms.

**vii. EXPECTED DURATION OF PARTICIPATION OF EACH TOPIC**

Considering the inclusion period (01/01/2016 – 31/12/2018), the ambispective nature of HF and the planned postoperative follow-up, the duration of participation for a subject will be a maximum of 1 medium-term follow-up (minimum 4 years postoperatively) for patients implanted between 2016 and 2018.

**viii. NUMBER OF REQUIRED TOPICS TO BE INCLUDED IN THE CI**

Over the period of implantation under consideration (01/01/2016 – 31/12/2018), 120 patients were implanted with a SAGITTA® EVL-R rod in the investigation center selected for HF and can potentially be included. Only patients who meet the screening criteria and agree to participate (inclusion) will be included and their data collected.

**ix. INCLUSION PERIOD**

The implementation period considered for the HF is retrospective and extends from 01/01/2016 to 31/12/2018 for the centre in question.

Inclusion of subjects will occur as patients travel to their follow-up visit. Inclusions will be carried out in 5 months, corresponding to the time needed to reconvene all patients.

**x. TOTAL EXPECTED DURATION OF CI**

The study will begin once all the necessary opinions and authorizations have been obtained.

The total duration of the study depends only on its prospective part, which consists of monitoring the subjects in the medium term, at least 4 years postoperatively. Retrospective collection will be carried out as follow-up visits are made, as soon as the patient's consent is obtained. The total duration of the study will be 5 months for follow-ups, at the date of writing of this protocol.

**xi. RELATIONSHIP BETWEEN THE STUDY POPULATION AND THE TARGET POPULATION**

Due to the ambispective nature of HF, for which implantation of SAGITTA® EVL R rods has already been performed, implanted patients fit the target population. The selection criteria ensure that only subjects that exactly match the target population will be included in the CI.

## xii. VULNERABLE POPULATIONS, PREGNANT AND/OR BREASTFEEDING WOMEN

The target population of SAGITTA® EVL R rods as defined in Chapter 2.F.i does not include any vulnerable populations. In addition, the selection criteria as mentioned in chapters 6.C.i to 6.C.iii make it possible to ensure the non-inclusion of vulnerable patients and respect for the target population.

## D. PROCEDURES

### i. DESCRIPTION OF ANY HF-RELATED PROCEDURES TO WHICH SUBJECTS ARE SUBJECTED (INCLUDING DEVIATIONS FROM STANDARD CARE)

Only an additional procedure that is neither heavy nor invasive is required when participating in this HF compared to the standard care provided as part of the systematic follow-up during hip replacement revision surgery in the investigation center in question. Namely, a quality of life questionnaire (SHO-12 forgotten hip score) and a functional score (HHS Harris Hip Score) are requested in addition. These can be completed in part by the patient or collected by the investigator.

As far as the retrospective part is concerned, all the necessary data will be collected directly from the patients' medical records, the subjects having already undergone the following visits: preoperative visit, intervention, immediate postoperative follow-up. Depending on the date of the operation, one or more intermediate postoperative follow-ups may have been performed. Data on these interim follow-ups will not be collected. Only relevant data in terms of serious adverse events will be collected for these interim follow-ups.

For the prospective part, which concerns only the medium-term postoperative follow-up (minimum 4 years) taking place after the inclusion of patients in the study, the procedures to which the subjects participating in HF will be subjected are listed and briefly described below. These procedures are the same as those performed as part of the systematic follow-up of a hip replacement in the investigation center in question. At the end of the investigation, the subjects continue to be monitored according to the habits of the center.

### **Inclusion of subjects in the CI**

Patients scheduled for their usual follow-up visit will be selected (detailed process available in Chapter 13) and at the end of the screening process, the patient will be included if he or she consents to participate in the study.

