Ethical considerations	The investigation will be conducted in accordance with the investigation protocol, the regulations in force, including the Public Health Code as well as the Medical Devices Regulation 2017/745, the ISO 14155:2020 standard, as well as in accordance with the ethical principles described in the Declaration of Helsinki. The investigation will start as soon as the authorisations from the competent authorities are received in accordance with the typology of the study, category 4.1. As personal data will be collected and analysed during this investigation, SERF complies with the reference methodology MR 001 (declaration 2140288 v 0). The collection of personal data will also be in accordance with GDPR 2016/679. All data and information relating to patients or their participation in this study will be considered confidential and in accordance with applicable laws and regulations will not be made public. The data collected and stored in a pseudonymised format does not allow the identification of a patient through the data collected. Under no circumstances will the names of patients be transmitted or communicated to SERF.

	
Patient consent will be collected by the principal investigator or another surgeon in the department during the on-site follow-up visit.
 
As the EUDAMED database is not yet available, this study will be registered on the public database www.clinicaltrials.gov.

Main objective	
To evaluate the medium-term postoperative survival rate (minimum 4 years postoperatively) of SAGITTA® EVL R rods placed between 2016 and 2018, all causes of revision combined.

Secondary objective(s)	
The secondary objectives of this study are to:
 
 
- Study the survival rate by components and by etiology (revision and revision with reconstruction)
 
- Study the patient's satisfaction with his hip prosthesis
 
- Confirm the safety of these implants by studying any complications observed
 
- Evaluate performance through the clinical scores of HARRIS and forgotten prosthesis score of the revision femoral stems SAGITTA® EVL R.
 

Primary outcome	
The survival rate will be determined according to the Kaplan-Meier curve with the replacement of the femoral implant, all causes combined.

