Treatment(s)/procedure(s) related to the study	
Prospective part:
 
According to the centre's practice, as part of the systematic follow-up of hip replacement replacements, a clinical examination will be carried out with an assessment of any complications and patient satisfaction. Only a quality of life questionnaire (SHO-12) and the HHS score will be required by this HF in addition to the standard care practiced in systematic follow-up in this center. These questionnaires will be completed jointly by the patients and the surgeon (additional procedure that is neither heavy nor invasive).
 
Routine radiological evaluation will be performed. It allows the evaluation of osseointegration and bone reconstruction to document possible complications.
 
The collection of its data will be carried out in a paper case report form (CRF).
 
Retrospective part:
 
In accordance with the patient's agreement, retrospective data will be collected using the patient's medical record and will be collected in the CRF.
 
No additional examination to current practice will be carried out as part of this investigation.

Total duration of the study	The prospective portion of the study will last approximately 5 months depending on patient availability. The duration of each patient's participation in this study is limited to this single consultation. Retrospective data collection will be carried out simultaneously. This is a total duration of the study of 5 months.
Study timeline	The prospective part will begin as soon as regulatory approvals are obtained, scheduled for January 2023 and will be completed in May 2023. The retrospective part will be conducted after the patient consent has been collected. Study closure and report writing: July 2023
Statistical analysis	A statistical analysis will be carried out at the end of the study. This analysis will be carried out by SERF. A descriptive analysis will be done based on the data collected during the study. A follow-up of the events that occurred will be carried out, as well as an analysis of the survival rate according to Kaplan Meier.

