**ii. CRITERIA FOR NON-INCLUSION**

- Patient who have not expressed consent to the collection of their data and participation in the study,
- Patient unable to understand the surgeon's instructions or perform postoperative follow-up.
- Patient with a contraindication to the use of the SAGITTA® EVL R revision femoral stem
- Patient implanted with a SAGITTA® EVL R revision femoral stem outside of their indication

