## **E. SAMPLE SIZE**

According to the available data, 120 SAGITTA® EVL R revision rods were implanted at the Rouen University Hospital – Charles Nicolle Hospital between 01/01/2016 and 31/12/2018. The final sample size will reflect the current practice of the selected investigation center based on the patient base as observed over the inclusion period and meeting the selection criteria.

The total sample size will depend on the number of subjects who do not object to participation and data collection, the number of subjects who have died and have been lost to follow-up.

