# **13. PROCESS FOR OBTAINING NON-OPPOSITION**

## **A. GENERAL PROCESS FOR OBTAINING INFORMED CONSENT**

Informed consent is mandatory for studies meeting the Reference Methodology MR-001.

Prior to the first inclusion and in compliance with good clinical practices, the study investigator(s) are trained by the sponsor in the patient information process as well as in the collection of informed consent during the study set-up visit.

During a patient's visit planned as part of the systematic follow-up of hip replacements, the investigator offers to participate in HF if he or she meets the selection criteria.

To do this, the investigator provides the information relating to the oral test and gives the information letter (see Appendix 3). The investigator also answers any questions he may have. After the subject has been able to consider all the information and has been given the newsletter, and after the reflection period that has been given to him, he then has the choice to give his consent to his participation in the study and the collection of his data. The patient will be able to give consent from the moment he has received all the information until his next follow-up visit.

If the investigator expresses his or her consent, he or she obtains the consent in the form provided (see Appendix 3), of which he or she keeps the copy that he or she has imperatively dated and signed, in the investigator's binder, *and also gives a copy to the subject*. The patient is then included in the HF and considered as a "subject" participating in the HF. *The patient has time to think about it after the presentation of the study to give his or her agreement or not to his participation.*

A copy of the newsletter is given to the subject.

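### Entry needs consent from a living patient at least 4 years after surgery, so the primary survival figure describes living consenters, not the exhaustive 2016–2018 series

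*Protocol*

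**What the plan says.** **Entry.** Participation is offered at the medium-term visit, at least 4 years after surgery (Protocol, Section 1, study population; Sections 6.C.v and 6.D.i). Section 6.D.i states: "at the end of the screening process, the patient will be included if he or she consents to participate in the study". The synopsis places consent at the same point: "Patient consent will be collected by the principal investigator or another surgeon in the department during the on-site follow-up visit". Section 6.C.ii lists as a ground for non-inclusion: "Patient who have not expressed consent to the collection of their data and participation in the study". Section 6.C.viii adds: "Only patients who meet the screening criteria and agree to participate (inclusion) will be included and their data collected". Section 13.A is categorical: "Informed consent is mandatory for studies meeting the Reference Methodology MR-001".

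**Access to records.** The synopsis timeline says: "The retrospective part will be conducted after the patient consent has been collected". Section 6.C.x agrees: "Retrospective collection will be carried out as follow-up visits are made, as soon as the patient's consent is obtained".

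**Description of the cohort.** The synopsis says that all patients operated on at the centre with this stem, about 120, will be included, and it calls the series exhaustive and continuous. Section 6.A.ii calls the included cohort comprehensive and consecutive; Section 7.I.i calls it exhaustive.

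**Deaths and losses.** Section 6.D.iii expects them to be numerous. Section 7.C.iii counts lost, deceased and withdrawn subjects as censored in the Kaplan-Meier calculation.

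**Other wording on entry.** Section 7.E says: "The total sample size will depend on the number of subjects who do not object to participation and data collection". Section 7.F uses the same non-objection test, Section 9 mentions a non-opposition form, and the title of Chapter 13 speaks of non-opposition although its text requires consent.

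**Objective.** Section 5.C.i and the synopsis target all-cause survival of the stems inserted from 01/01/2016 to 31/12/2018, with at least 4 years of follow-up.

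**The concern.** A patient who died in 2019, or whom the centre can no longer reach, cannot consent in 2023. The records stay closed and the stem never enters the analysis, whether or not it was revised. The protocol nevertheless describes the included group as if every implanted patient were in it, and its survival formula lists the dead and the lost among the censored.

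What is at stake is what the primary figure means. The synopsis and Section 3.B use the result to confirm the performance and safety of the stem range. A reader told that the series is exhaustive will take the curve as survival of all stems implanted in the period. Under the entry rule it is survival in a group selected on being alive, reachable and willing at least 4 years later.

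**Working it through.** The protocol's 120 is a count with no calculation behind it, so there is no planned figure to reproduce. The check has four steps.

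**1. Follow-up of an included patient.** Inputs: implant dates 01/01/2016 to 31/12/2018 (Section 6.C.i); visits January to May 2023 (synopsis timeline).
- Shortest: 31/12/2018 to 01/01/2023 = 1,462 days / 365.25 = 4.00 years.
- Longest: 01/01/2016 to 31/05/2023 = 2,707 days / 365.25 = 7.41 years.

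**2. What this does to the estimate.** The estimator is the product of (1 − D/N) over the removal times. If nobody is censored before year 4, the product up to year 4 reduces to 1 − (removals before year 4)/(number included). Hypothetical example: 85 included, 9 removals before year 4, all censoring between 4.0 and 7.4 years. Kaplan-Meier at year 4 = 1 − 9/85 = 0.894, the plain proportion. Beyond year 4, censoring operates in the usual way.

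**3. How far the included group could differ from the implanted series (illustration).** Let r be the true revision proportion and q the participation of revised patients divided by that of unrevised patients. The apparent revision proportion is r·q / (r·q + 1 − r). The documents do not give q; the range 0.5 to 2.0 is assumed. For r, the 15.2% five-year revision rate in Section 3.A serves as one crude value, so true survival is 84.8%.

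| q | Apparent revision | Apparent survival | Shift (points) |
|---|---|---|---|
| 0.5 | 0.076/0.924 = 8.2% | 91.8% | +7.0 |
| 0.8 | 0.1216/0.9696 = 12.5% | 87.5% | +2.7 |
| 1.0 | 15.2% | 84.8% | 0 |
| 1.25 | 0.19/1.038 = 18.3% | 81.7% | −3.1 |
| 2.0 | 0.304/1.152 = 26.4% | 73.6% | −11.2 |

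**4. Bounds without a participation model.** Suppose 84 of 120 are included (assumed) and 13 are revised (84 × 0.152 = 12.8, rounded).
- Included group: 71/84 = 84.5% unrevised.
- Worst case, all 36 absent patients revised: 71/120 = 59.2%.
- Best case, none of the 36 revised: 107/120 = 89.2%.

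For scale, the half-width of the protocol's own 95% interval at 15.2% and n = 84 is 1.96 × √(0.152 × 0.848/84) = 7.7 points. That interval does not cover the uncertainty about absent patients.

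**The case against.** **The protocol discloses it.** Section 6.D.iii names deaths and losses as affecting interpretation, Section 7.E says they reduce the sample, and Section 6.C.viii calls the 120 only potentially includable. That is fair, but none of these passages says that such patients are absent from the survival curve, and the word exhaustive says the opposite.

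**The objective is already limited to at least 4 years of follow-up.** It can be read that way. Even so, it does not mention being alive and consenting, and the cohort labels remain wrong.

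**The censoring definition is not an error.** This largely stands. Section 13.A lets a patient take time before consenting, the schedule in Section 6.A.iv puts inclusion before the medium-term visit, and Section 10.B foresees a missed visit. A consented subject could therefore be lost or die. The rule is close to empty before year 4, not wrong.

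**The figures are illustrations.** This stands. The participation ratios are assumed and include no bias. The 15.2% is a five-year figure that the document does not tie to stem removal or change. With r = 7.5% (also assumed), q = 2 gives 0.15/1.075 = 14.0%, a shift of about −6.5 points rather than −11.2.

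Two stronger readings are tempting. A reader might infer from the mix of consent and non-objection that analysts could build different risk sets. The operative passages do not support this: data are collected only after consent, so non-consenters have nothing to analyse. A reader might also infer that lost patients would distort the curve because only serious adverse events are taken from interim visits (Section 6.D.i). The protocol provides no route by which such patients enter.

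**Conclusion.** The point holds as a mismatch between the entry rule and the population the protocol says it describes. Patients who died or became unreachable before the 2023 visit cannot enter, so the included group is not exhaustive or consecutive. The year-4 Kaplan-Meier estimate is close to the unrevised share of living, attending consenters. This follows from the consent passages and the dates alone.

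It does not follow that the survival figure is too high. The estimate is biased for the implanted series only if death, loss or refusal is related to revision, and the documents settle neither size nor direction. A living patient whose stem has already been revised can still attend and consent, so the selection is on being alive, attending and agreeing, not directly on keeping the stem. The study has no test or success criterion (Sections 7.D and 7.G), so no formal decision changes. What changes is which population the primary figure may be said to describe.

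**What to change.** **Recommended.**
- State the primary result as stem survival among patients alive and consenting at 4 years or more.
- Remove exhaustive, comprehensive and consecutive as descriptions of the included group (synopsis; Sections 6.A.ii and 7.I.i), and correct the synopsis statement that all operated patients will be included.
- Report aggregate counts from about 120 implanted to included: dead, lost, refused, attended. A best-case/worst-case bound as in step 4 is an optional addition.
- Align the non-objection and non-opposition wording (Sections 7.E, 7.F and 9; Chapter 13 title) with the consent rule.

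This costs wording and a flow count; no visit or procedure is added. The downside is a more qualified primary figure.

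**Alternative, only if the ethics and data-protection framework allows.** Enter deceased and unreachable patients from hospital records, with time zero at implantation. Collect the last known stem status with its date, and censor at death or that date. This needs record look-up, one added data item and probably an amendment with ethics review, and Section 13.A may rule it out. It would still assume that censoring is unrelated to revision. In a simulation set to 15.2% revision at 5 years, with 30% dead or lost before year 4 and twice the revision hazard in that group (all assumed), true 4-year survival was 87.6%. Entering everyone gave 88.8%; the included group alone gave 90.4%. The error shrinks but does not vanish.

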### **Follow-up visits**

The follow-up visit will take place as follows: the subject meets the investigator for the systematic clinical examination as carried out in the investigation center, with a search for signs indicating the possible presence of a complication in the operated hip and the evaluation of the patient's satisfaction. The pain experienced by the subject will be reported via the HHS score. HHS and SHO-12 functional scores are collected by the investigator via the appropriate questionnaires submitted to the patient (see Appendices 5 and 6 and section 6.A.iii). Bone reconstruction and osseointegration are evaluated on the X-ray performed prior to the follow-up visit to document a complication. If a revision, removal or change of implant is necessary or in the case of the detection of a complication, the investigator records this in the patient's file.

### **Summary of the Study**

#### 1. Identification of eligible participants:

During a medium-term postoperative follow-up consultation (minimum 4 years) in orthopedic surgery (performed as a clinical routine) for patients implanted with a SAGITTA® EVL R revision rod during the period under consideration, they will be offered to participate in the study

2. Information and collection of consent from people agreeing to participate in the medical consultation
3. Acquisition of clinical data during the follow-up visit
4. End of participation for the participant.

**ii. DESCRIPTION OF ACTIVITIES CARRIED OUT BY THE PROPONENT'S REPRESENTATIVES (EXCLUDING MONITORING)**

The sponsor's representatives carry out the following tasks prior to the start of the CI (obtaining all necessary authorisations):

- Selection, definition of roles and responsibilities and verification of the necessary experience of the various stakeholders and collection of possible conflicts of interest;
- Documentary preparation of the study and obtaining the necessary authorizations through the required regulatory submissions;
- Registration of the CI on a public database.

During the conduct of the study, the proponent's activities are:

- Documentation of exchanges between stakeholders as well as competent authorities in charge of CI;
- Evaluation of adverse events reported by the investigator and transmission of the required information to the competent authorities in charge of the HF, as well as to other stakeholders;
- Drafting, documentation of any amendments, as well as obtaining the necessary authorizations if applicable;
- Update if necessary the risk analysis of HF according to the complications observed;
- Communication with investigators of HF advancement;
- Collection of questions from investigators, transmission and documentation of answers to investigators.

When the HF is completed (last visit to last follow-up of the last patient), the sponsor is responsible for the following activities:

- Closure of the CI according to the procedures provided;
- Carrying out the analysis of the data generated;
- Issue of the investigation report.

The monitoring activities for which SERF is responsible are discussed in §6.E.

